1. TITLE

Comparison of two exercise approaches for the management of low Back pain in the emergency department setting.

SHORT TITLE

Comparison of two exercise based physiotherapy approaches in treatment of low back pain.

3. SETTING

Emergency department, Royal Brisbane and Women's Hospital (RBWH)

4. BACKGROUND INFORMATION

Acute low back pain (LBP) is a common presentation to the emergency department (ED). It is also a major health condition associated with high rates of absenteeism from work and more frequent use of health services ¹. As per the international back pain guidelines, primary contact practitioner aim is to classify back pain and rule out serious pathology ⁸. The mechanical low back pain group (back pain from a musculoskeletal cause) makes up 90% of presentations to ED.⁹ Currently in ED standard treatment comprises of ¹⁴⁻¹⁶

1. **Standard Care in ED (RMO/ED registrar, or Physiotherapist):** Assessment of symptoms, physical and radiological investigations as appropriate for the individual and the provision of a diagnosis. Management will include patient education and assurance ¹¹, symptom relief by analgesia (NSAIDS, paracetamol & opioids if necessary), as well as recommendation to stay as active as possible including return to work ¹². Depending on their response to the analgesia patients are discharged with Physiotherapy follow-up ⁸.

2. Additional treatment when seen by the Physiotherapist in ED:

The commencement of spinal stabilisation¹⁰ and mobility exercises while in the ED because poor spinal stability and altered movement patterns have been shown to be a potential cause and/or effect of low back pain²⁸. Alternatively a McKenzie exercise protocol may be provided but only if the Physiotherapist has appropriate training in this method.

Despite these forms of care twenty five percent (RBWH EDIS statistics) of low back pain patients are admitted to the short stay unit for overnight analgesia due to difficulties coping with the pain. They are then discharged after 1-2 days. Apart from adding to the cost ³, this also blocks a bed for other emergency patients. Patients who are admitted utilise health resources while those who are discharged are not followed up by physiotherapists for 1-3 weeks (due to the public hospital waiting list). This causes a delay in initiating formal assessment and treatment, sometimes leading to representation to ED. Effective treatment of acute LBP is important because it prevents patients from developing chronic LBP which needs more costly and complex investigations and treatment. The key point is that currently for patients presenting to ED with back pain treatment lacks an individualised approach with respect to alleviating mechanical low back pain. We propose this may be improved with the use of a McKenzie approach to management of back pain in the ED setting.

The McKenzie method of mechanical diagnosis & therapy is an active exercise approach involving repeated movements, sustained positions and therapeutic forces, it has an educational component with the purpose of minimising pain, disability, and improving spinal mobility ⁴. This method involves the assessment of symptomatic and mechanical responses to repeated movements and sustained positions. The responses are used to classify them into subgroups or syndromes (Posture, Dysfunction and Derangement) which help in guiding the treatment principles ⁴⁻⁶. Of the large number of classification schemes developed in the last 20 years, the McKenzie Method has the greatest empirical support (i.e. validity and reliability) among the systems based on clinical features². This approach utilises exercises specifically to promote rapid symptom relief based on the patient's individual clinical presentation¹⁷. Therefore we propose this approach is of potentially great value in an ED where patients present primarily due to an episode of significant back pain.

The McKenzie approach unlike other therapeutic methods aims to make the patient as independent of the therapist as possible⁷, thus preventing representations to ED. The McKenzie method of treatment has shown better results than other physical therapy procedures in some acute, sub-acute and chronic low back pain presentations^{5,6}. In particular a high-quality randomised trial in which treatment was based on this approach showed larger reductions in pain²⁷ and disability²⁶ and promoted faster return to work in patients with acute LBP than other conservative therapy recommended by the clinical guidelines¹³. We propose that the 'McKenzie exercise' approach may be a more effective 'additional physiotherapy' intervention for patients seen by physiotherapists in the ED setting then the more standardly used muscular 'stability/mobility exercise' training.

Therefore the purpose of this study is to compare if more benefits are gained with a 'McKenzie exercise' approach compared to a 'stability/mobility' exercise approach for patients who are treated by a Physiotherapist for low back pain in ED. We anticipate the findings of the study will be informative to the best approach to

management of these patients in ED, and may be informative to guide appropriate professional development for physiotherapists who work in ED.

5. STUDY AIM AND HYPOTHESIS

AIM: To compare the additive clinical benefits (pain, disability, re-admission) of a McKenzie exercise approach (Mechanical Diagnosis and Therapy) versus a stability/mobility exercise approach, to that of usual care for patients who are managed by physiotherapists for their low back pain to ED, both in the immediate (immediately following intervention within ED), and short-term (2 weeks following ED consultation) time points.

Hypothesis: A McKenzie exercise approach (Mechanical Diagnosis and Therapy) will have greater additional benefits (pain, disability, re-admission) for patients who present with low back pain to ED than will a stability/mobility exercise approach, both in the immediate (immediately following intervention within ED), and short-term (2 weeks following ED consultation) time period.

Null Hypothesis: The McKenzie exercise approach will have no beneficial effects compared to the stability/mobility exercise approach for patients who present with low back pain to ED either in the immediate (immediately following intervention within ED), and short-term (2 weeks following ED consultation) time period.

6. STUDY DESIGN

This is a randomised clinical trial comparing the additive clinical benefits (pain, disability, re-admission) of a McKenzie exercise approach (Mechanical Diagnosis and Therapy) versus a stability/mobility exercise approach, to that of usual care, for patients who are managed by physiotherapists for their low back pain in ED. Outcomes will be evaluated both in the immediate (immediately following intervention within ED), and short-term (2 weeks following ED consultation) time points. Outcomes will conducted by an assessor blinded to the group allocation of the participant and as both forms are exercise based intervention participants will be blinded to their intervention group.

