8. OUTCOME MEASURES

Primary Measure

Low back Pain – This will be measured with a Numeric pain score form $(0-10)^{19,20,21}$.

Secondary Measures

Pain Related Disability - Roland Morris low back pain disability score (RDQ) ^{18,22}. The RDQ and ODI scores are highly correlated, with similar test–retest reliability and internal consistency²³. Good internal consistency is reported for the RDQ, with Cronbach's alpha ranging from 0.84–0.96²².

The primary and secondary measure will be handed and collected on the initial presentation by a non-participating clinician (nurse on duty), it will be handed over in a sealed coded envelope to the principal investigator. The associated investigators

([name] and [name]) performing the initial intervention will be blinded towards these scores.

Re-presentation to the emergency department (ED)

Re-presentation to ED and any medical/allied health input sought by the patient during the next two weeks (asked over the telephone by the follow-up Physiotherapist) will also be recorded and analysed.

The clinician (Physiotherapist – [name]) making the two week telephonic follow-up will be blinded towards the group status and the initial presentation details of the patient.

All scoring sheets will be handed to the principal researcher in a sealed coded envelope to be opened for data analysis.

Adherence to the prescribed exercise program will be recorded on a two week checklist (copy attached), exercise diagrams will be provided to both groups (copy attached). Patients will be advised on the number of repetitions and daily frequency which will be recorded by the patient on the two week checklist provided. The checklist will be returned to the principal investigator by a reply paid envelope (funded by the principal researcher)

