10. STUDY PROCEDURE

Participant recruitment and consent process: The patients presenting to the emergency department are triaged by nursing staff, assessed by medical staff/Physiotherapist and accordingly given analgesia. After 30 minutes of receiving analgesia, the patient will be approached by the Physiotherapist and given information regarding the study and if the patient is agreeable, written consent will be obtained.

Baseline outcome measures: The initial pain score (0-10), Roland Morris score will be recorded by the patient themselves without any guidance from the investigator. They will be handed over by a non-participating clinician (nurse on duty).

Group allocation process: Patients will then be randomised to one of the two groups via sealed envelopes (concealed allocation picked by non-participating medical/nursing staff).

Intervention: The participant will then be assessed for lumbar range of motion, neurological status, lumbar stability and mobility. Depending on the group the patient belongs, exercise will be performed under supervision. The participant will be provided with exercise sheets and checklist for home. Participants will be offered follow-up Physiotherapy two weeks after discharge in a public or private setup depending on his/her preference and availability of private cover.

Follow-up outcome measures: The two week telephonic follow-up to record the pain score, Roland Morris disability score will be obtained by a non-participating Physiotherapist. The exercise check-list provided to the patient on discharge, will be returned to the principal investigator by a reply paid envelope funded by the principal investigator. Patients are unaware of the follow-up process and thus will not feel as if they are being offered special treatment to participate in the study.

Resource impact on service: There will be negligible impact of services in ED as both treatment types are presently being used by Physiotherapists in treatment of LBP patients in ED at RBWH. Some of the outcome measures are not routinely done in ED will only take an additional 20-30minutes to complete without any clinician time being utilised. The referral process will not add to the workload to peripheral hospitals as the patient would normally be referred anyway.

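### The aim, hypothesis and design promise pain and disability outcomes immediately after the ED intervention, but the procedures schedule these scores only before randomisation and at 2 weeks

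*Protocol*

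**What the plan says.** Protocol section 5 sets the aim and hypothesis for three outcomes (pain, disability, re-admission), "both in the immediate (immediately following intervention within ED), and short-term (2 weeks following ED consultation) time period". The null hypothesis names the same two times. Section 6 repeats them as the design: "Outcomes will be evaluated both in the immediate (immediately following intervention within ED), and short-term (2 weeks following ED consultation) time points". It also says that the outcome assessor is blinded to group.

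The collection steps are in sections 8 and 10. Section 8 describes the forms at entry: "The primary and secondary measure will be handed and collected on the initial presentation by a non-participating clinician (nurse on duty". Section 10 describes the same baseline step: "The initial pain score (0-10), Roland Morris score will be recorded by the patient themselves without any guidance from the investigator". Allocation comes next: "Patients will then be randomised to one of the two groups via sealed envelopes". Treatment follows: "Depending on the group the patient belongs, exercise will be performed under supervision". The participant then receives exercise sheets and a checklist to take home. The next score is at two weeks: "The two week telephonic follow-up to record the pain score, Roland Morris disability score will be obtained by a non-participating Physiotherapist".

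Section 8 records re-presentation over the two weeks after the visit, asked at the same call. Section 11 adds a between-group comparison of admission to the short stay unit, which section 8 does not list as an outcome measure.

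**The concern.** A trial can only test an immediate effect on pain if someone records pain after the treatment and before the patient goes home. Sections 5 and 6 commit the trial to that test. Sections 8 and 10, which say who hands out which form and when, contain no such step.

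The immediate effect matters to this trial. Section 4 justifies the McKenzie approach in ED largely by rapid symptom relief in patients who attend because of severe pain. A score not taken before the participant leaves ED cannot be recovered later, and no statistical analysis plan can analyse it. If staff notice the gap during recruitment and improvise a score, it will have no defined timing, form or collector, and the blinded assessment promised in section 6 will not be assured for it.

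**Working it through.** The point rests on comparing sections of the text, so the main check sets them side by side.

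**Step 1. Order of events in section 10, with the scores scheduled at each step**

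| Step | Pain score (0-10) | Roland Morris score |
|---|---|---|
| Triage, assessment, analgesia, consent | none | none |
| Baseline measures, self-completed | yes | yes |
| Randomisation by sealed envelope | none | none |
| Supervised exercise, then home sheets and checklist | none | none |
| 2-week telephone call | yes | yes |

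Section 8 describes the same two collections and no third.

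**Step 2. Can an existing score serve as the immediate outcome?** The baseline score cannot, because it precedes both randomisation and exercise. The 2-week score is the other promised time point. The home checklist records adherence to the exercises, not pain or disability.

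**Step 3. Outcomes and times promised in section 5, against what is scheduled**

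| Outcome | Immediate | 2 weeks |
|---|---|---|
| Pain (primary) | not scheduled | scheduled |
| Disability | not scheduled | scheduled |
| Re-admission | as defined in section 8, counted over two weeks, so not an immediate outcome | scheduled |

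The one outcome close to the ED visit is short stay unit admission in section 11. It gives some information on the immediate period but is neither a pain nor a disability score.

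**Step 4. Does the sample size settle which pain time point is meant?** Inputs, from the sample size paragraph at the end of section 7.2: difference 2, SD 2.5 (reading the ± 2.5 as a standard deviation), two-sided 0.05, power 0.80.

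n per group = 2 × (1.960 + 0.842)² × (2.5 / 2)² = 2 × 7.85 × 1.5625 = 24.5, rounded up to 25.

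This reproduces the stated 25 per group, with power 80.7% by the normal approximation. By the t-test the requirement is 25.5, so 26 per group, and 25 gives 79.1%; the difference is immaterial. The calculation is for one comparison of two means and names no time point. Section 8 names the pain score as primary, also without a time. The figure is therefore sound, but the document does not say whether it refers to the immediate or the 2-week score.

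**The case against.** The best counter-argument is that the protocol's silence does not prove that no score is taken. Sections 8 and 10 are not exhaustive: short stay unit admission is analysed in section 11, yet neither section says how it is recorded. Section 6 is part of the plan too, and it says that outcomes will be evaluated immediately after the intervention. On this view the protocol has merely left out how and by whom the score is obtained. This is fair as far as it goes, and it is why the conclusion is limited to what is scheduled. It does not remove the problem. For pain and Roland Morris scores, sections 8 and 10 do give timing, form and collector at baseline and at 2 weeks, and give none for the immediate score. Staff following section 10 would not collect it.

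The repeated measures ANOVA in section 11 does not imply a third measurement either. It names no times, and baseline plus 2 weeks is enough for a comparison over time.

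Three stronger readings are tempting, and the document does not support them:

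- A reader might infer that the immediate period has no data at all, or that overnight stays go unexamined. Section 11 compares short stay unit admission between groups, so the gap concerns pain and disability scores only.
- A reader might infer conflicting success rules, because the hypothesis speaks of both times while the null, about the McKenzie arm, is worded differently: "will have no beneficial effects compared to the stability/mobility exercise approach for patients who present with low back pain to ED either in the immediate". This is loose wording for no effect at either time. Neither sentence is written as a decision rule.
- A reader might infer inflated type I error or reduced joint power from two time points. That would require separate tests at each time with a stated rule for combining them. The protocol gives no such rule and plans a repeated measures ANOVA, or a Kruskal-Wallis test if the data are not normal.

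**Conclusion.** The inconsistency stands. Sections 5 and 6 promise immediate pain and disability outcomes, while sections 8 and 10 schedule those scores only before randomisation and at 2 weeks. Followed as written, 0 of the 50 planned participants would have an immediate post-intervention pain or Roland Morris score, and the immediate hypothesis could not be tested for the primary outcome or for disability. Re-admission, as section 8 defines it, cannot be an immediate outcome.

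The reach is limited. The 2-week comparisons of pain, disability and re-presentation remain answerable, the sample size reproduces for a single comparison, and short stay unit admission gives some information near the ED visit. The conclusion assumes that the sequence in section 10 is what staff will follow, with no unstated collection step. The protocol also leaves open which pain time point is primary. That choice belongs to the investigators, and nothing in the document decides it.

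**What to change.** Choose one of two routes before enrolment.

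**Keep the immediate time point.** In section 10, after the supervised exercise and before the participant leaves ED, add one 0-10 pain score. It should be self-completed and sealed in a coded envelope as at baseline, and collected by a nurse who did not draw the allocation envelope. That last condition is needed because section 10 lets non-participating nursing staff pick the envelope, while section 6 promises blinded assessment. In section 5, limit the immediate time point to pain and attach disability and re-admission to 2 weeks only. In section 8, state which pain time point is primary and say that the sample size refers to it.

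**Or drop it.** Delete the immediate time point from sections 5 and 6, and state in section 8 that the primary pain score is the one at 2 weeks.

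The first route costs one question per participant, about a minute of patient time by estimate, by a collection route already in place, plus the need to have a second nurse available. Limiting it to pain avoids repeating the whole set of forms, for which section 10 allows an additional 20-30 minutes. The second route costs only wording, but gives up the question about immediate pain relief. Neither changes the treatment.

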7. PARTICIPANTS

Fifty participants (25 in each exercise group) will participate in the study.

7.1 INCLUSION CRITERIA

Low back pain (LBP) – atraumatic onset. Age - 20-50 years Gender - Male and/or Female

7.2 EXCLUSION CRITERIA

History of substance abuse eg: IV drug user (IVDU), ETOH Spinal fractures.

Pregnant women

Neurological compromise (as shown by loss of strength, sensations and reflexes).

Red flags eg: loss of weight, fever, history of cancer.

Multiple medical co-morbidities (chronic obstructive pulmonary disease, ischemic heart disease, chronic kidney disease, uncontrolled diabetes and hypertension).

Patients brought in by police who are under influence of illicit drugs and alcohol.

Patients bought in by police who will remain in custody.

Patients with known cognitive and intellectual disability (decided on the basis of information collected by the triage nurse).

Patients having an acute concurrent systemic illness.

Patients with congenital spinal structural deformity.

Patients unable to provide consent and comply with the home exercise program.

Sample size was calculated on the primary outcome measure Numeric pain score . To calculate a sample size between two independent means for a two tailed test at a significance of less than 0.05, a power of ≥ 0.8 for the outcome measure (pain score) a conservative minimum clinically important difference of 2 (± 2.5) was used^{19,20, 21}. This predicted that 25 patients in each group would be required.

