12 WITHDRAWAL FROM STUDY PARTICIPATION

In accordance with the Declaration of Helsinki, each subject has the right to withdraw from the study at any time. An investigator also has the right to withdraw subjects from the study in case of any adverse effect, lack of compliance or reasons concerning the subject's wellbeing.

In case of withdrawal, the subject will continue to receive standard care in ED and follow-up as appropriate. Clinical notes will be documented for the same

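### The 25 per group calculated as required is also the number enrolled, with no allowance for loss, so the stated power of at least 0.8 holds only with complete data

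*Protocol*

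**What the plan says.** The sample size is justified in the last paragraph of Protocol section 7.2. The basis is the pain score: "Sample size was calculated on the primary outcome measure Numeric pain score". The test compares "two independent means for a two tailed test at a significance of less than 0.05", with "a power of ≥ 0.8 for the outcome measure (pain score"). The effect is given as "a conservative minimum clinically important difference of 2 (± 2.5) was used". The conclusion is: "This predicted that 25 patients in each group would be required".

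Section 7 sets enrolment at the same number: "Fifty participants (25 in each exercise group) will participate in the study".

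The protocol states no expected loss rate, no inflation for loss and no replacement of lost patients. Two other places bear on completeness. Section 10 has the follow-up score collected remotely: "The two week telephonic follow-up to record the pain score, Roland Morris disability score will be obtained by a non-participating Physiotherapist". Section 12 says that "each subject has the right to withdraw from the study at any time", and it also lets an investigator withdraw a subject, for example for an adverse effect or lack of compliance.

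**The concern.** A sample size calculation gives the number of patients who must contribute an outcome to the comparison. Here that number and the number enrolled are identical, so the claimed power rests on every randomised patient having a pain score at the time of analysis. One of the two time points named in sections 5 and 6 is a telephone contact two weeks after an ED visit, and the protocol itself foresees withdrawals.

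The power figure is the protocol's only justification for its size. If it is quoted later as though it had been assured, a non-significant result could be given more weight as evidence of no difference than 50 patients, or fewer, can support.

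**Working it through.** **Inputs from section 7.2:** difference 2 points; ± 2.5 read as the standard deviation (the text does not label it, but this reading reproduces the stated number); two-sided alpha 0.05; power 0.80. From section 7: 25 per group, equal allocation. **Assumed:** loss of 10% or 20%, equal in both groups; the protocol gives no rate.

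**1. Reproducing the protocol's figure (normal approximation).**

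n per group = 2 × (1.960 + 0.842)² × (2.5 / 2)² = 24.53, rounded up to 25.

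At 25 per group the standard error is 2.5 × √(2/25) = 0.707 and the standardised difference is 2 / 0.707 = 2.83. Power = Φ(2.83 − 1.96) = 0.807. The stated 25 is confirmed. A one-sided test would have given 20, so the two-tailed statement also fits.

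**2. The same inputs with the t distribution.** Using the noncentral t with 48 degrees of freedom, noncentrality 2.83 and critical value 2.011, power at 25 per group is 0.791. The first group size to reach 0.80 is 26 (0.808).

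**3. Power when outcomes are missing.** For group sizes n₁ and n₂, the standard error is 2.5 × √(1/n₁ + 1/n₂). The t-test power follows from the noncentral t with n₁ + n₂ − 2 degrees of freedom. The half-width of the 95% confidence interval is the t critical value times the standard error.

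| Patients with an outcome | Power, t-test | Power, normal | 95% CI half-width |
|---|---|---|---|
| 25 and 25 (complete) | 0.791 | 0.807 | 1.42 |
| 25 and 24 (one lost) | 0.783 | 0.799 | 1.44 |
| 24 and 24 (one lost per group) | 0.774 | 0.791 | 1.45 |
| 23 and 23 (8% lost) | 0.756 | 0.774 | 1.49 |
| 22.5 per group (10% lost) | 0.746 | 0.765 | 1.50 |
| 20 per group (20% lost) | 0.693 | 0.716 | 1.60 |

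The second row needs no assumed rate: one missing outcome is enough to put power below 0.80 by either formula, though only just by the normal one.

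**4. Enrolment that would keep 25 per group with an outcome.** 25 / (1 − 0.10) = 27.8, so 28 per group (56 in total). 25 / (1 − 0.20) = 31.25, so 32 per group (64 in total).

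**The case against.** The strongest reply is that the protocol's calculation is correct. Its inputs give 24.53, 25 is the right rounding, and power by the usual formula is 0.807. This stands. A reader might infer from the t-based figures that section 7.2 contains an arithmetic error. It does not: 26 against 25, or 0.791 against 0.80, is a choice of formula and would not be worth raising alone.

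Second, a reader might infer that any loss at all brings power down to 0.75 or 0.69. The table does not support that. One or two lost patients leave 0.77 to 0.78 by t-test, and the lower figures need 10% to 20% loss. The protocol gives no rate, follow-up is a single call after two weeks, and section 7.2 excludes patients who cannot comply with the home programme. Section 11 specifies intention to treat, and section 12 does not say that withdrawn patients' outcomes are lost. The size of the loss is therefore unknown. What remains is that even a very small loss falls outside the stated power.

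Third, the protocol does not fix two weeks as the primary time point. Section 8 names pain as primary without a time, and sections 5 and 6 name an immediate comparison in the ED as well. Loss by telephone bears on the 2-week comparison; the immediate one would be little affected. This stands and limits the point.

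Fourth, section 11 plans a between/within repeated-measures ANOVA, which may have different power from a comparison of two independent means. That is true, but the direction cannot be told from the protocol. With a baseline and one follow-up, the group-by-time test is a comparison of change scores. If 2.5 is the standard deviation of the raw score, the standard deviation of change is 2.5 × √(2(1 − ρ)). At 20 per group this gives power 0.55, 0.69 or 0.89 for a baseline to follow-up correlation ρ of 0.3, 0.5 or 0.7. The protocol gives no correlation, so the planned analysis cannot be relied on to make up the shortfall.

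**Conclusion.** The point holds as a missing allowance for loss, not as an error of calculation. The stated power of at least 0.8 is met only with complete data, and then only by the normal approximation (0.807; 0.79 by t-test). One lost patient takes it to 0.783 by t-test or 0.799 by the normal approximation. At an assumed 10% or 20% loss, the 2-week comparison has power of about 0.75 or 0.69 by t-test, and 0.77 or 0.72 by the normal approximation.

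These figures assume that ± 2.5 is a standard deviation, that loss is equal in the two groups, and that the test is the comparison of two independent means on which the protocol sized the trial. The shortfall is modest and does not threaten the trial. It is still worth correcting, because the protocol states the power as a minimum and its own enrolment figure leaves no room for it.

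**What to change.** Keep 50 participants. In the sample size paragraph of section 7.2, replace the claim of at least 0.8 with wording such as:

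> With 50 randomised, two-sample t-test power to detect a 2-point difference (SD 2.5, two-sided 0.05) at 2 weeks is about 0.79 with complete data, 0.75 at an assumed 10% loss and 0.69 at an assumed 20% loss; the result will be read from the 95% CI (half-width about 1.4 to 1.6 points).

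Do not add power figures for a baseline-adjusted analysis: section 11 does not plan one, and the protocol gives no correlation on which to base them.

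The cost is a change of wording and a slightly less favourable stated power; no further patients are needed. If the sponsor prefers to keep 25 per group with an outcome, about 28 to 32 per group would have to be enrolled at 10% to 20% loss, which is 6 to 14 more patients in total.
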